## PROTOCOL SUMMARY

Title:	Validation of shade, a wearable ultraviolet light monitor, for reduction of actinic keratosis
Summary:	
The incidence of non-melanoma skin cancers, due to increased ultraviolet (UV) exposure, has increased by 300% over the past 2 decades. The innovative UV sensor, Shade, is designed to help people manage their UV exposure by quantifying their UV exposure levels through a linked smartphone application. In order to validate the effectiveness of Shade, we propose conducting a study communicating the level of UV exposure and correlating it with the development of actinic keratosis (AK), a precancerous lesion of the skin. We will recruit patients with multiple AKs. We will include renal transplant patients as this population develop AKs as well. We will evaluate the UV monitor's effectiveness in decreasing the number of AKs over a summer. This randomized partially blinded study will recruit 120 patients with a recent history of AKs and evaluate the incidence of new AKs after one summer. We will perform a control versus study group analysis. Half of the subjects (study group) will be randomly assigned to use the sensor along with its smartphone application, while the other half (control group) will receive standard of care treatment involving counseling to avoid sun exposure. Subjects will have regular standard of care visits with the dermatologist who will follow the number of actinic keratosis via clinical exam and photography. The primary outcome will be a statistically significant reduction by at least 25% of the cumulative number of newly occurred AK lesions between the control and the study group over one summer, counted at enrollment and follow-up. In subjects at one study site, skin DNA damage will also be assessed using cyclobutane pyrimidine dimers (CPD) levels measured by ELISA in both sun exposed (nose) and sun protected skin (buccal mucosa) in both the study and control groups. Secondary outcomes will look at clinical decreases by 25% in CPD levels after using the sensor.

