## 4 STUDY DESIGN AND ENDPOINTS

### 4.1 DESCRIPTION OF THE STUDY DESIGN

This randomized partially blinded study will recruit 120 patients with a history of actinic keratosis (AK) lesions. A control versus study group analysis will be performed where 50% of the subjects will be randomly assigned (balanced by Fitzpatrick skin type, separate randomization lists will be made for type I&II and types III-VI, at time of first visit subjects will be assigned to study or control group by giving them the next assignment on the appropriate list) to use the SHADE sensor and its app (study group), while the other 50% (control group) will receive standard of care UV counseling(placebo). Subjects will have 3 visits. The first and last visit will be standard of care visits at 0 month (enrollment), and the conclusion of their involvement. The second visit will be scheduled 3 months after the enrollment visit. The final visit will be scheduled as soon as practical, but at least 3 months after visit 2 and after September 30. On arrival at each visit, study personnel will pre-screen patients to ensure that the sensor is not visible to physician prior to examination, for example by placing it in their pocket. At each follow up visit, the number of actinic keratosis on the face and hands will be counted and photographed. They will be treated as per standard of care protocol with cryotherapy or curettage. General use of field therapies will not be permitted during the trial. Any lesions suspicious of non-melanoma or melanoma skin cancer will be photographed and biopsied as part of the standard of care algorithm. Cyclobutane pyrimidine dimers (CPD) levels will be measured by ELISA from exposed (cheek) and unexposed (buccal mucosa) skin scrapings collected at the first and last visit. For each patient, the CPD level from exposed skin will be normalized to the sun protected CPD level measured from unexposed skin. We will compare the normalized CPD level of control versus study participants at each timepoint and their average CPD change over time.

We will then compare these levels with Shade UV measurements. Finally, patients will also answer questions in PROMIS (Patient-Reported Outcomes Measurement Information System) in the fields of anxiety, depression and ability to participate socially to gauge their attitudes toward the sensor

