### 7.3.7 SCHEDULE OF EVENTS TABLE

Procedures	Prior to enrollment	Enrollment	Visit 1	Before visit 2	Visit 2	Before visit 3	Visit 3	AE Visit
Screening call	X							
Screening questions		X						
Informed consent		X						
Medical history		X						
Patient survey			X		X		X	
Dermatology Visit			X		X		X	
UV counseling			X		X		X	
Full Skin Check			X		X		X	
Focused Skin Check			X		X		X	
Collect skin scraping (WCM only)			X		X		X	
Randomization			X					
Compliance engagement				X		X		
Return study materials							X	
Condition driven medical exam								X

Screening call:

Screening questions: These are listed in the CRF

Informed consent: As approved by IRB

Medical history: Key questions listed in CRF

Patient survey:

Dermatology visit:

Collect skin scraping:

Randomization:

Compliance engagement:

Return study materials: See section 7.9

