**#6 (Secondary): Test the correlation between measured UV exposure and the number of new nonmelanoma skin cancers.**

We will test the correlation between the cumulative UV exposure and the number of new nonmelanoma skin cancers using a Pearson correlation test or a non-parametric Spearman test if the requirements for the parametric test are not met. A significant correlation will be defined as  $p > 0.2$  and  $p\text{-value} < 0.05$ . UV exposure will be defined as the cumulative UV exposure in erythemally-weighted  $\text{J/m}^2$  at each time point since enrollment.

**#7 (Secondary): Quantify the impact of Shade on keratinocyte DNA damage approximated by the measurement of cyclobutane pyrimidine dimers by ELISA.**

Cyclobutane Pyrimidine Dimers (CPD) are induced by UV exposure in a dose dependent fashion. UV exposure can lead to immediate CPD increase; therefore measurement of CPD following the delivery of a known UV dose allows for a biological readout of UV effects. In addition, CPD levels represent an equilibrium between UV induced formation and DNA repair; therefore, they can also reflect chronic UV exposure.

CPD level will be measured from ELISA from exposed (cheek) and unexposed (buccal mucosa) skin samples collected. For each patient, the level from exposed skin will be normalized to the basal CPD level measured from unexposed skin. Correlation of CPD level to Shade UV measurement 24 hours prior to collection will allow for an acute UV biological validation that Shade measured UV levels correspond to levels of CPD damage (using Pearson correlation test or a non-parametric Spearman test). We will also compare the normalized CPD level of control versus study participants at each timepoint and their average CPD change over time using a t-test. These comparisons will assess the accuracy of Shade measurements as it relates to chronic UV exposure.

The outcome will be a statistically significant reduction by at least 25% of the normalized CPD level of exposed keratinocytes.

**#8 (Secondary): Quantify the impact of Shade on patients' quality of life assessed by PROMIS (Patient-Reported Outcomes Measurement Information System) in the fields of anxiety (Mental Health), depression (Mental Health), and Ability to Participate in Social Roles and Activities (Social health).**

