### 10.6.1 ENROLLMENT/ RANDOMIZATION/ MASKING PROCEDURES

The randomization schedules will be developed prior to the enrollment of the first subject. There will be one schedule for Fitzpatrick types I-II and a second schedule for Fitzpatrick types III and higher. The randomization schedule is a simple list of assignments to the groups 'Treatment,' meaning that the subject will be given the Shade device and mobile application and 'Control,' meaning that the subjects will be given only the standard of care counseling to avoid UV. The following sequence of events at enrollment will ensure that the treating physician will be blinded to the subject assignment:

- (1) visit with study coordinator for screening, informed consent, and medical history.

If the subject passes screening and grants consent

- (2) physician visit.

During the physician visit, the study coordinator will take the next randomization from the randomization schedule. This schedule will be prepared by the sponsor in such a manner that the coordinator remains blind to the next assignment until it is requested. The sponsor has latitude to implement this using any reasonable physical or computational system. The subject assignment will be entered on the randomization schedule available only to the study coordinator and the study monitor.

- (3) wrap up conversation with study coordinator.

After the physician visit the study coordinator will sit with the subject in a separate room. The next visit or visits will be tentatively scheduled. If the subject is in the treatment group, the device will be provided and either the coordinator or a sponsor representative will work with the subject to setup the mobile application and ensure that subject understands how to use the device.

At subsequent visits subjects in the treatment group will be instructed to

- (1) avoid discussing their assignment with the physician.
- (2) place the shade sensor in a purse or pocket out of view of the physician
- (3) mention to the study coordinator if the subject of the assignment came up in conversation with the physician.

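### Endpoint #7 sets a 25% CPD success rule without saying which of its listed between-arm tests decides it, and the Protocol Summary words it more loosely still

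*Combined protocol and SAP*

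**What the plan says.** The success rule in 10.4.3, #7 reads "The outcome will be a statistically significant reduction by at least 25% of the normalized CPD level of exposed keratinocytes". That sentence names no visit, contrast or scale. Two sentences earlier the same block lists the tests: "compare the normalized CPD level of control versus study participants at each timepoint and their average CPD change over time using a t-test". Sections 4.1 and 7.1.1 list the same pair of comparisons and also give neither precedence.

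The Protocol Summary puts the outcome differently: "Secondary outcomes will look at clinical decreases by 25% in CPD levels after using the sensor".

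Other passages that bear on the reading:

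- Section 10.2 states the general hypothesis as less sun damage in the treatment group. Section 10.4.1 sets two-sided tests at 0.05. Section 10.4.9 says that no multiple comparisons are involved.
- The device is issued only after the physician part of the first visit. Section 10.6.1 says of the wrap-up meeting that "If the subject is in the treatment group, the device will be provided", and 7.3.2 agrees.
- On the last sample, 4.1 says "The final visit will be scheduled as soon as practical, but at least 3 months after visit 2 and after September 30".
- The sampling visits differ between sections. Section 4.1 has "skin scrapings collected at the first and last visit". The schedule in 7.3.7 marks scrapings at visits 1, 2 and 3, and the tube labels in 7.2.3 allow all three. The analysis table in 10.4.10 has two CPD columns, at 0 and 12 months.
- CPD is measured at one site only. No sample size, standard deviation or power is given for it.

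**The concern.** A pass/fail rule needs one contrast attached to it. Here up to four between-arm tests could carry it: visit 1, visit 2 if it is sampled, visit 3, and change from visit 1 to visit 3. The visit 1 test cannot show an effect of Shade, because nobody has used the sensor yet. The visit 3 level and the change are both legitimate comparisons of randomised arms, but they can give different answers in the same trial. The plan also does not say what 25% means for a change score, that is, 25% of which quantity.

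The Summary wording adds a further ambiguity. Read literally, a fall from before to after sensor use would satisfy it, even if controls fell by the same amount.

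At stake is whether the DNA-damage result can be stated as met or not met without a choice made after the data are seen.

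**Working it through.** **1. Plan's own figure.** There is none for CPD. The only stated power, 0.81 with 50 per arm, is for the actinic keratosis endpoint and says nothing about CPD. Everything below therefore uses assumed inputs: lognormal normalised CPD, CV 0.5 to 1.0, within-patient correlation r of 0.3 to 0.7, and 30 to 60 patients per arm. The upper limit is 120/2 = 60. The one-site subset may be smaller.

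**2. Why level and change can disagree.** With SD s at each visit and n per arm, the variances of the estimated arm difference are:

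- visit 3 level: 2s²/n
- change: (2s²/n) × 2(1 − r)
- visit 3 adjusted for visit 1 (ANCOVA): (2s²/n) × (1 − r²)

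Relative to the level test, for r = 0.3, 0.5 and 0.7:

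- change: 1.40, 1.00, 0.60
- ANCOVA: 0.91, 0.75, 0.51

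The correlation between the level and change estimates is √((1 − r)/2) = 0.59, 0.50, 0.39, so the two tests are far from interchangeable.

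**3. True 25% effect at visit 3, no seasonal shift.** Disagreement means that exactly one of the two t-tests (level, change) is significant in favour of Shade. By simulation this happens in 20 to 39% of trials with 30 or 50 per arm, and in roughly 15 to 40% over the whole range up to 60 per arm.

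**4. No effect: how often does some between-arm test meet the full rule?** The full rule is p < 0.05, in the right direction, with an observed reduction of at least 25%. With 50 per arm, the standard error of a relative difference is about CV × √(2/50) = CV × 0.2.

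- CV 0.5: SE 0.10. The 25% threshold lies 2.5 SE out, beyond 1.96, so it is the binding condition and makes passing by chance rare.
- CV 1.0: SE 0.20. Significance alone needs 1.96 × 0.20 = 39%, so the threshold adds nothing. Each test passes in the right direction with probability of about 0.025, and four tests can reach at most 4 × 0.025 = 0.10.

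Simulation of all four tests gives about 0 to 5% at CV 0.5 and 6 to 9% at CV 1.0. The visit 1 test alone contributes 0 to 2%.

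**5. The before-after reading.** This needs two assumptions that the plan does not make: a paired test within the study arm, and a seasonal shift common to both arms. With no device effect, 60 study-arm patients and r = 0.5, the rule is met with these probabilities:

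- seasonal fall of 25 / 30 / 40%: 0.50 / 0.86 / 1.00 at CV 0.5, and 0.46 / 0.66 / 0.93 at CV 1.0
- no seasonal fall: about 0.01 or less
- seasonal rise of 30%: about 0

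Under the same seasonal falls, the arm comparison at visit 3 meets the rule in 0.1 to 2.5% of trials.

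**6. One better contrast.** Since 1 − r² is at most 1, and at most 2(1 − r), the adjusted analysis is never less precise than either t-test, apart from one degree of freedom. As a hand check on the log scale, s² = ln(1 + CV²) and the effect is ln 0.75 = −0.288. With 50 per arm the level test has SE 0.472 × 0.2 = 0.094 (CV 0.5), giving power of about 0.86, or 0.833 × 0.2 = 0.167 (CV 1.0), giving about 0.41. Simulated power over CV 0.5 to 1.0 and r 0.3 to 0.7:

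- ANCOVA: 0.42 to 0.99
- level test: 0.40 to 0.87
- change test: 0.29 to 0.97

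**The case against.** The strongest defence is that the comparator is not really missing. The arm-versus-arm tests stand just before the rule, 4.1 repeats them, 10.2 puts the hypothesis between arms, and the endpoint is worded as the impact of Shade. No within-arm CPD test is planned anywhere. The Summary phrase is a single loose sentence, and the sentence before it says that both groups are sampled. All of this stands: a between-arm reading is the natural one. It does not settle which between-arm test carries the 25%.

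Three stronger conclusions are tempting, and the documents do not support them.

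- A reader might infer an error rate of about three times 0.05. The chance that at least one of the four tests has p < 0.05 under no effect is indeed 0.14 to 0.16. That figure counts results favouring control and ignores the 25% threshold. In favour of Shade alone it is 8 to 9%, and under the full rule it is the lower range in step 4. It also includes visit 2, which 4.1 and 10.4.10 do not sample.
- A reader might infer that the plan would credit a seasonal fall to the sensor. That needs the unplanned paired test and a fall of assumed direction and size. The month of visit 1 is not fixed, 6.1.9 gives 9 to 12 months of use, and 10.4.10 labels the last sample 12 months, so little shift or a rise is equally open.
- A reader might see the visit 1 test as a serious source of false claims. It adds little, and a difference that predates the device could hardly be presented as its effect.

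It is also fair to say that part of the level-versus-change disagreement is simply noise in a small sample, and that this is a secondary, single-site biomarker. The primary conclusion on actinic keratoses is unaffected.

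**Conclusion.** The point holds as a failure to designate the deciding analysis. Endpoint #7 attaches a 25% rule to several unranked between-arm tests, one of which predates the intervention, and the Summary phrase is loose enough for a fall shared by controls to fit it.

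If Shade truly lowers CPD by 25%, the level and change tests would disagree in roughly 15 to 40% of trials. If it does nothing, some between-arm test meets the full rule in about 0 to 5% (CV 0.5) to 6 to 9% (CV 1.0), which is at or modestly above the nominal level. These figures depend on the assumed CVs, correlations and subset sizes, none of which the documents supply. The absence of a named contrast does not depend on them. The change should be made, but it is not critical to the trial's main result.

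**What to change.** In 10.4.3, #7 and in the Protocol Summary, state one deciding analysis: the study-versus-control difference in normalised CPD at the final visit, adjusted for the visit 1 value by ANCOVA, for example on the log scale. Express the 25% as a reduction relative to control on that scale (a ratio of 0.75 or lower), and say whether it applies to the point estimate or to a confidence limit.

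Then:

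- use visit 1 CPD only as baseline, with no between-arm efficacy test at that visit;
- label the change comparison, and any visit 2 comparison, as supportive;
- replace the Summary phrase with a lower level in the study group than in the control group at the final visit;
- report before-after changes descriptively, for both arms side by side, with no success rule attached;
- reconcile the CPD sampling visits in 4.1, 7.2.3, 7.3.7 and 10.4.10.

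The cost is a few sentences, with no new samples, visits or patients. The small downside is that a before-after fall, or an isolated result at one timepoint, can no longer count as meeting the outcome.

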##### **#3 (Secondary): Quantify the impact of Shade on the numbers of new cutaneous squamous cell carcinomas confirmed by histology during follow up over the study period.**

To test the early effect of Shade on skin cancer risk and the robustness of our findings, we will perform a longitudinal analysis to test a reduction by at least 25% of squamous cell carcinoma. The effect of Shade use will be estimated using a single mixed linear model (with random intercept and slope) for repeated (longitudinal) data including study group and time since enrollment as explanatory variables. A similar stepwise multivariate approach with backward selection as described in the primary aim will be performed to take into account confounding factors.

**#4 (Secondary): Quantify the impact of Shade on the number of new nonmelanoma skin cancers (basal cell carcinomas, cutaneous squamous cell carcinomas) confirmed by histology over the study period.**

To test the early effect of Shade on skin cancer risk and the robustness of our findings, we will compare the cumulative numbers of new nonmelanoma skin cancers between the control and study group and test a reduction by at least 25% of non-melanoma skin cancer s as secondary outcome, using a t-test. A similar stepwise multivariate approach with backward selection as described in the primary aim will be perform to take into account confounding factors.

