To assess the impact of Shade on quality of life, patients will be surveyed using short form paper versions of PROMIS (Patient-Reported Outcomes Measurement Information System) scores in the fields of depression, anxiety, and the ability to participate in social roles and activities. PROMIS survey will be performed at each visit. We will compare the change in PROMIS scores between group and study using a t-test at each time-point.

The outcome will be assessed for statistical significance (p-value of change in PROMIS score between groups) and clinical significance (changes of 3 points on a single score are generally considered meaningful to subjects).

**#9 (Secondary): Assess sensor usage in the study patient population and compare characteristics of observant vs non-observant and responsive vs non-responsive patients.**

To assess sensor usage, we will estimate the overall percentage (and 95% confidence interval) of days used in the study patient population, the average (and standard deviation) and median (and quartile) of the daily UV threshold set by the patients and the percentage of days below and above the UV threshold.

The Shade sensor and the mobile application enables users to decide, by looking at self-reported symptoms and daily cumulative UV exposure over 15 and 30 days, how much UV exposure in J/m^2 they would like to manage per day, which we call the daily UV threshold. Users can select a daily UV threshold that is lower than their previous maximum daily UV exposure. Of course, users are free to go beyond this threshold if they chose to and the app will let them know in real time by how much they have exceeded their threshold. The threshold can be adjusted at any time through the app. The Shade app does not make any recommendation regarding the daily threshold. Note that each subject will be individually counseled to minimize UV exposure.

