## 10.4.10 TABULATION OF INDIVIDUAL RESPONSE DATA

Clinical data tables will be reduced into a table of individual responses for analysis as follows:

Column	Source (name of CRF with data)
SubjectID	N/A
AK baseline (count)	Actinic Keratosis
AK follow up (cumulative count)	Actinic Keratosis
NMSC baseline (count)	NMSC
NMSC follow up (cumulative count)	NMSC
Observant % of days	Compliance database
Responsive Y/N	Shade database: days with UV limit below 90% of exposures
CPD R 0	Lab data
CPD R 12 month	Lab data
MHA 1	PROMIS MHA visit 1
MHA 2	PROMIS MHA visit 2
MHA 3	PROMIS MHA visit 3
MHD 1	PROMIS MHD
MHD 2	PROMIS MHD
MHD 3	PROMIS MHD
SHP 1	PROMIS SHP
SHP 2	PROMIS SHP
SHP 3	PROMIS SHP
UV Ave	Sensor data
AE (count)	CRF
comment	

group	Randomization
exclude	

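### PROMIS and CPD are compared without adjustment for baseline: valid under randomisation, but less precise than the visit 1 values already collected would allow

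*Combined protocol and SAP*

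**What the plan says.** **PROMIS (section 10.4.3, #8).** Three domains are surveyed: "PROMIS survey will be performed at each visit". The analysis is: "We will compare the change in PROMIS scores between group and study using a t-test at each time-point". A change exists only at visits 2 and 3, so there are two tests per domain. The benchmark for clinical relevance is that "changes of 3 points on a single score are generally considered meaningful to subjects". Section 10.4.10 already holds the baseline in the analysis table (for anxiety, the source is "PROMIS MHA visit 1"), with matching columns for depression and social participation.

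**CPD (section 10.4.3, #7).** The plan will "compare the normalized CPD level of control versus study participants at each timepoint and their average CPD change over time using a t-test". Levels are thus compared at each timepoint and change is compared once. Success is a significant reduction of at least 25% in the normalised level; the plan does not say which of these tests decides it. Section 4.1 has "skin scrapings collected at the first and last visit", and section 10.4.10 has two CPD columns (0 and 12 months), whereas the schedule in section 7.3.7 marks scrapings at all three visits.

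**Adjustment elsewhere.** Endpoints #1 to #4 have a covariate step; for #3 it reads "A similar stepwise multivariate approach with backward selection as described in the primary aim will be performed to take into account confounding factors". Neither #7 nor #8 has such a sentence, and the general approach in section 10.4.1 adds no rule that would reach them.

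**The concern.** A change score subtracts the baseline, which fixes its slope at 1. Unless the correlation between baseline and follow-up is perfect, the best slope (with equal variances) is r, which is below 1. Subtracting too much adds baseline noise to the comparison. A last-visit level test, as planned for CPD, goes the other way and fixes the slope at 0. Regression on the baseline estimates the slope and is at least as precise as either, apart from the one degree of freedom spent on it.

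At stake is the width of the confidence intervals for quality of life and DNA damage. This matters for PROMIS because the benchmark is only 3 points and the documents state no power for it. Randomisation is stratified by skin type alone (section 10.6.1), so nothing balances PROMIS or CPD at visit 1. A chance difference there carries into the change score with opposite sign, in proportion to 1 − r.

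**Working it through.** **The plan's own figure.** The only stated power is 0.81 for the primary AK endpoint (section 10.5). None is given for PROMIS or CPD, so there is no figure to reproduce here.

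**Inputs from the documents.** 120 patients, half to each arm, so nominally 60 per arm (section 4.1); two-sided 0.05 (section 10.4.1); 3-point PROMIS benchmark (section 10.4.3, #8).

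**Assumptions not in the documents.** r from 0.3 to 0.8; PROMIS SD from 6 to 10; equal variances at baseline and follow-up; no dropout.

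**Formulas, per-subject variance in units of SD².**
- Follow-up level only: 1
- Change score: 2(1 − r)
- Baseline-adjusted (ANCOVA): 1 − r²
- ANCOVA relative to change: (1 − r²) / [2(1 − r)] = (1 + r)/2

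The change-score sample equivalent to 60 per arm under ANCOVA is 60 / [(1 + r)/2].

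| r | Change | ANCOVA | Ratio | Equivalent n per arm | Extra per arm |
|---|---|---|---|---|---|
| 0.3 | 1.40 | 0.91 | 0.65 | 60/0.65 = 92 | 32 |
| 0.5 | 1.00 | 0.75 | 0.75 | 60/0.75 = 80 | 20 |
| 0.7 | 0.60 | 0.51 | 0.85 | 60/0.85 = 71 | 11 |
| 0.8 | 0.40 | 0.36 | 0.90 | 60/0.90 = 67 | 7 |

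Below r = 0.5 the change score is noisier than follow-up alone. Above 0.5 it gains from the baseline, but less than ANCOVA does.

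**Power for a 3-point PROMIS difference, 60 per arm (change score, then ANCOVA; normal approximation).**

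| r | SD 6 | SD 8 | SD 10 |
|---|---|---|---|
| 0.3 | 64%, 82% | 41%, 58% | 28%, 41% |
| 0.5 | 78%, 89% | 54%, 66% | 38%, 48% |
| 0.7 | 94%, 97% | 76%, 82% | 56%, 63% |
| 0.8 | 99%, 99.5% | 90%, 93% | 74%, 78% |

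A simulation at SD 10 (4,000 trials per setting) agrees: 28% against 40%, 37% against 47% and 57% against 63% for r of 0.3, 0.5 and 0.7.

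**Interval width at SD 10, r = 0.5.** Change: 1.96 × 10 × √(2/60) = 3.6 points. ANCOVA: 3.6 × √0.75 = 3.1 points.

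**Chance imbalance at SD 10.** The SE of the baseline difference is 10 × √(2/60) = 1.8, so a gap of 2 points or more in either direction (z = 1.1) arises about 27% of the time. Given a 2-point gap and r = 0.5, the expected change-score difference moves by (1 − 0.5) × 2 = 1 point, a third of the benchmark.

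**CPD.** The same ratio applies to the change test if variances are equal. Against the last-visit level test, ANCOVA has 0.91, 0.75, 0.51 and 0.36 of the variance for r of 0.3, 0.5, 0.7 and 0.8. No power or patient count can be given: scrapings are taken at one site only (protocol summary; section 7.3.7), and neither the number of subjects there nor an SD is stated.

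**The case against.** A reader might infer that the plan discards the baseline or that its PROMIS comparison is biased. The documents do not support that. A change score uses the baseline, and over randomisations its t-test is unbiased and targets the same between-arm difference as ANCOVA. The imbalance effect above is conditional on the gap that happens to occur. Nor is testing visits 2 and 3 separately an error: each test is valid for its own contrast, and a repeated-measures model is a tidier alternative.

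A reader might also infer that CPD change is t-tested at every visit, or that the patient counts carry over to CPD. Neither holds: section 10.4.3, #7 tests levels at each timepoint and change once, and the base of 60 per arm is not the CPD sample.

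The size of the gain is open to challenge. No r appears in the documents, and at high r the gain is small. Equal variances are doubtful for CPD, because enrolment dates vary while the final visit must fall after September 30. Even for PROMIS, 60 per arm is an upper figure: section 5.4.2 restricts each endpoint to complete data, and #9 excludes patients with sensor use below 15% of days. These are also secondary endpoints. All of this stands. It limits the size and weight of the point but does not remove the gain, which under equal variances is present for every r below 1.

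**Conclusion.** The point holds as one of efficiency. PROMIS is analysed by unadjusted change-score t-tests, and CPD by unadjusted tests of level and change, although the baselines are in the analysis table. For PROMIS, adjustment would cut the variance by 35% to 10% for assumed r of 0.3 to 0.8, worth about 32 down to 7 patients per arm on a nominal 60, and would remove the dependence on a chance baseline gap. This rests on assumed r and equal variances; the power figures also rest on an assumed SD. For CPD the direction is the same but the size cannot be stated. The planned tests are valid and the primary conclusion is unaffected. The change is worth making because it is nearly free.

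**What to change.** **PROMIS (#8).** For each domain, fit one linear repeated-measures model to the visit 2 and visit 3 scores, with arm, visit, arm × visit, baseline score and skin-type stratum. Name the adjusted visit 3 difference as the main result and report it with a 95% CI against the 3-point benchmark.

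**CPD (#7).** Replace the change t-test and the last-visit level t-test with one ANCOVA of last-visit normalised CPD on arm, baseline normalised CPD and skin-type stratum. A log scale is optional; it gives a ratio that can be set directly against the 25% criterion. Drop the between-arm test at the first visit, which precedes any use of the device and cannot show an effect of it. Reconcile sections 4.1 and 7.3.7 on whether a visit 2 scraping is taken.

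**Timing.** State that the visit 1 survey and scraping are completed before allocation is disclosed. Section 7.3.7 puts both in the same visit as randomisation, and the sequence in section 10.6.1 does not place the survey.

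**Cost.** Plan wording, plus confirming the order of events at visit 1. No new data, visits or patients.
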